- 2. Baseline Testing.** There are three test visits. Visit 1 is an inpatient visit that includes a hyperinsulinemic-euglycemic clamp procedure, adipose tissue and muscle biopsies, Arginine stimulation test, and a 12-h urine collection. An activity monitor will be provided to the participant that will be worn for the proceeding 7 to 10 days. Visit 2 is an outpatient visit where dual-energy X-ray absorptiometry and magnetic resonance imaging/elastography scans will be performed and muscle strength will be assessed. Visit 3 is another inpatient visit that involves a modified 3-h oral glucose tolerance test and the first dose of study pill ingestion. A stool sample will also be returned to the study team at Visit 3. The scans performed during visit 2 may be performed at a different or separate visit, depending on scheduling availability and participant preference.
- 3. Randomization.** Randomization will be conducted in a double-blind fashion with both the participants and members of the research team blinded to group assignment.

4. **Intervention period.** During the 16 weeks of the treatment period, participants will be seen by the research coordinator and/or one of the study investigators each week. At each visit at WU, compliance will be recorded based on an unused pill count.
5. **Repeat testing.** All baseline testing will be repeated after participants complete 16 weeks of treatment.

A. Background and Significance

Nicotinamide mononucleotide is a key intermediate for nicotinamide adenine dinucleotide (NAD⁺) biosynthesis

Nicotinamide adenine dinucleotide (NAD⁺) is a co-substrate for NAD⁺-consuming enzymes that are essential in the regulation of diverse biological processes, including metabolic function, inflammation and aging [1-4]. In mammals, NAD⁺ is synthesized from nicotinamide (NIC) and nicotinic acid (two different forms of vitamin B₃) and tryptophan (Figure 1). Nicotinamide is considered the major precursor of NAD⁺. Nicotinamide mononucleotide (NMN) is a key NAD⁺ intermediate which is synthesized from NIC by nicotinamide phosphoribosyltransferase (NAMPT), a rate-limiting NAD⁺ biosynthetic enzyme. Nicotinamide riboside (NR) is also converted to NMN by nicotinamide riboside kinases (NRKs). NMN is converted to NAD⁺ by three NMN adenylyltransferases (NMNATs). Synthesized NAD⁺ is used by NAD⁺-consuming enzymes, such as sirtuins (SIRT1-7), poly (ADP-ribose) polymerases (PARPs), and cyclic ADP ribose hydrolase (CD38), and redox reactions.

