Little is known about NAD⁺ biology and NMN therapy in people. Data from preliminary studies we recently conducted in human subjects show that enhanced NAD⁺ biosynthesis is associated with metabolic health in people: i) adipose tissue NAD⁺ content is lower in people with obesity than people who are not obese (Figure 3A); ii) 16% weight loss induced by lifestyle (diet and exercise) therapy improved insulin sensitivity and β -cell function and decreased intrahepatic triglyceride (IHTG) content and caused a concomitant increase in skeletal muscle gene expression of a key NAD⁺ biosynthetic enzyme, NAMPT, in people with obesity and T2D (Figure 3B); and iii) 20% bariatric surgery-induced weight loss, which improved insulin sensitivity, β -cell function, and adipose tissue inflammation and decreased IHTG content in people with extreme obesity [20], also increased NAD⁺ concentrations in adipose tissue (Figure 3C). Although NMN is present in a variety of natural foods, including broccoli, tomatoes, avocado, and beef [14], the daily amount of NMN that is normally consumed as part of a healthy diet is very small. We found that ingestion of a single 250 mg dose of NMN, which is at the upper end of the dose typically taken by consumers, caused a rapid but transient increase in plasma NMN concentrations (Figure 4A) but caused more than a 3-fold increase in peripheral blood mononuclear cell (PBMC) NAD⁺ content within 60 minutes (Figure 4B). The dose of NMN used in the proposed study is 300 or 450 mg/day.

Summary. Data obtained from preclinical studies we conducted in rodent models and our preliminary studies conducted in people support the therapeutic potential of enhancing NAD⁺ biosynthesis to ameliorate metabolic dysfunction in people. In fact, NMN supplementation is commercially available, and is advertised to improve health and reverse aging, without evidence of these effects in people. The goal of this proposal is to fill this important gap in our knowledge by using a systems biology research approach, within the context of a randomized, placebo-controlled trial, to determine whether the beneficial effects of NMN on metabolic function, mitochondrial function and inflammation observed in rodents applies to people. In addition, we will evaluate for potential sex differences in the efficacy of NMN supplementation (observed in studies conducted in rodents) by studying a balanced number of men and women in each group.

B. Objectives/Specific Aims/Hypotheses

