C.3.4. Intervention. Placebo and NMN capsules will be provided at no cost by Shinkowa Pharma (Mirailab Bioscience Inc.) (Tokyo, Japan) under a Material Transfer Agreement (MTA) between Washington University School of Medicine (WUSM) and Shinkowa Pharma Co. Ltd. Capsules (placebo and NMN) will be shipped to us in sealed bottles and upon receipt stored in a locked room access limited to a small number of research team members under the responsibility of the PI. Study participants will be provided with either placebo or NMN pills by CTRU metabolic kitchen at WUSM after completing baseline testing. Daily consumption of the placebo or NMN pills will continue throughout repeat testing after 16 weeks of treatment. Study participants will be contacted via phone by the research coordinator weekly to help ensure compliance with the study protocol and problem-solve any barriers (such as introducing use of a pill organizer and daily log sheet if study pills are not being taken on a regular basis). Monthly follow-up study visits for participants will be held at WUSM. Medical monitoring of participants will be performed by the study Research Nurse Practitioner in consultation with the PI, as needed throughout the entire study period. In addition, a mid-intervention blood test (CBC and CMP) will be performed at approximately week 8 of intervention at WUSM. Participants will be provided with dietary supplementation diary to keep track of the daily supplementation record and asked to bring this handout to each intervention visit. Participants will be asked to maintain their physical activity level and body weight during the study period. A Supplement Accountability Log will be used to document dispensing of the dietary supplement or placebo to the participant and the return of unused product. Participants will be instructed to keep a study pill diary and return unused supplement at each scheduled WU study visit and at the end of the study. Compliance will be assessed by a study dietary supplementation diary and pill count.

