C.3.5. Accountability of dispensing placebo and NMN capsules. A Supplement Accountability Log will be used to document the dispensing of the dietary supplement or placebo to the participant and the return of unused product by the participant to WU. The Supplement Accountability Log will document the participant ID, the amount of supplement and the date supplement was dispensed to the participant, and the amount of supplement and date that the study participant returned. Participants will be instructed to return unused supplement at every scheduled WU study visit and study end at WU. The study research coordinator will perform a pill count and document in the Supplement Accountability Log at each WU study visit.

C.3.6. Data safety monitoring. All participants will be contacted by the research coordinator and/or research nurse weekly throughout the study. All safety and medical issues will be reviewed by [name], and, if needed, will be discussed with the participant's primary physician.

C.3.7. Repeat testing. All studies performed at baseline will be repeated after participants complete at least 16 weeks of treatment. Daily placebo or NMN dosing will continue throughout the repeat testing period, which will take ~2 weeks (weeks 16-18 of treatment).

C.3.8. Calculations.

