mixing room, by a certified pharmacy technician who completes annual recertification through BJH Pharmacy and is also GMP certified. Careful aseptic techniques will be used when inserting the catheters and when obtaining blood samples to decrease the risk of infection. In addition, continuous safety monitoring will be completed by [name] (PI) on a bi-monthly basis in person or remotely. All laboratory data and adverse events will be collected by the research nurse practitioner and the research investigator and will be reviewed and discussed by [name] (PI).

At time of informed consent each participant will be assigned a unique participant identifying number (study ID) and the link between ID and PHI will be kept in the REDCap. Consent forms and any other paper forms for the study will be stored in a locked filing cabinet in the office

The study ID is not related information about the individual and is not capable of being translated so as to identify the individual. Data and biological samples collected from study participants during the study participation will be labeled with the study ID and will *not* be used in combination with any personal identifiable information (PII).

All of the requested information as part of this study including PHI will be treated confidentially, protected from improper use and disclosure and will not be reused or disclosed to any other person or entity, except as required by law, for which the use or disclosure of the requested information would be permitted by the HIPAA Privacy Rule.

The use of 38 U.S.C. 7332 Information is to conduct scientific research and that no personnel involved may identify, directly or indirectly, any individual patient or subject in any report of such research or otherwise disclose patient or subjects in any manner.

The PII obtained from human subjects will only be available to individuals approved by WUSM IRB (only after participant signed WU informed consent form). Subject research records will be secured in areas under the 2-key lock concept (e.g., in a locked cabinet with access limited to the study team members in a locked room) at WUSM (Suite 301 at IWJ building). Electronic records (e.g., computer files and database) that contain PHI will be stored on firewall-protected secured servers at WUSM facilities that require approved access authorization.

Data Transfer/Sharing Plan

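### The last CBC/CMP that the supplied text names is at about week 8, roughly halfway through dosing, and Section D specifies no safety comparison

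*Combined protocol and SAP*

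**What the plan says.** Before treatment, Section H puts CBC, CMP, HbA1c and PT-INR in the medical screening. Step 1 of the Overview likewise places blood tests at the screening visit, as part of deciding eligibility.

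During treatment, C.3.4 adds that "a mid-intervention blood test (CBC and CMP) will be performed at approximately week 8 of intervention at WUSM". The same section states that "Daily consumption of the placebo or NMN pills will continue throughout repeat testing after 16 weeks of treatment", and C.3.7 puts that repeat testing at weeks 16-18.

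At the end of treatment, the Overview says: "All baseline testing will be repeated after participants complete 16 weeks of treatment". C.3.7 says much the same: "All studies performed at baseline will be repeated after participants complete at least 16 weeks of treatment". Neither sentence mentions safety bloods.

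Other monitoring continues throughout. There is weekly contact (C.3.6), medical monitoring by the nurse practitioner as needed (C.3.4), and blood pressure and adverse-effect evaluation (Section H). Section H also says that laboratory data and adverse events are collected and reviewed, and that "continuous safety monitoring will be completed by [name] (PI) on a bi-monthly basis in person or remotely".

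The outcome list in C.3.1 has no safety outcome. Section D describes analyses of baseline characteristics, the metabolic outcomes and the sex interaction, and no safety analysis.

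**The concern.** Efficacy is measured at weeks 16-18, after the full course. If the CBC and CMP are not repeated then, the trial has laboratory safety values only from about the middle of the exposure. A change in liver, renal or blood-count values that developed later and caused no symptoms would not show in those panels, and the two arms could not be compared on them at the exposure for which efficacy is reported.

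This matters more here because the background section itself says: "Little is known about NAD⁺ biology and NMN therapy in people". A 16-week placebo-controlled comparison is a good opportunity to collect such data, and an end-of-treatment value cannot be recovered once a participant has finished.

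**Working it through.** The plan gives no figure for laboratory safety coverage, so there is none to reproduce. The check has two parts.

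**1. Share of dosing after the last named draw**

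Inputs:
- L, the week of the draw: about 8 (C.3.4). No window is given, so I assume 7 to 9 to show the range.
- T, the end of dosing: week 16 to 18 (C.3.7).

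Formula: share = (T - L) / T.

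| Draw at week | Dosing ends week 16 | week 17 | week 18 |
|---|---|---|---|
| 7 | 9/16 = 56% | 10/17 = 59% | 11/18 = 61% |
| 8 | 8/16 = 50% | 9/17 = 53% | 10/18 = 56% |
| 9 | 7/16 = 44% | 8/17 = 47% | 9/18 = 50% |

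At week 8 exactly the share is 50% to 56%. With the assumed window it is 44% to 61%.

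A further draw at week 16 would leave (16 - 16)/16 = 0% to (18 - 16)/18 = 11%. A draw at the last repeat visit would leave none.

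**2. Does the repeat-testing clause already include CBC and CMP?**

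- The Overview makes screening (step 1, with blood tests) and baseline testing (step 2, three test visits) separate steps. Its step 5 and C.3.7 repeat what was done at baseline.
- C.3.2 introduces its procedures as those done before and after the intervention. It then lists, for Visit 1, the clamp, biopsies, NMN pharmacokinetics, arginine test and sleep measures. Visit 2 has MRI/MRE and strength. Visit 3 has the glucose tolerance test, first-dose pharmacokinetics and stool. Neither CBC nor CMP is named.
- Section H gives the screening panel the purpose of excluding people at increased risk, which is an eligibility purpose.
- C.3.4 names the week-8 panel explicitly, so where the authors wanted a safety draw on treatment they wrote it down.

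Read literally, the clause does not reach CBC and CMP. A site following the text would draw neither at weeks 16-18.

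**The case against.** The strongest reply is that silence is not absence.

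- **The visit lists are incomplete.** Plasma inflammatory markers are secondary outcomes (C.3.1) and are assayed (C.3.9), yet no visit description names a draw for them.
- **Screening and baseline overlap.** C.2 places DXA at the screening visit, the Overview places it at Visit 2, and it is an outcome of treatment. The repeat clause might therefore reach screening measurements, including CBC and CMP.
- **Some text is not in view.** Sections F (Timeline) and G (Foreseeable Risks) are in the table of contents but not in the supplied text, and the figures are not shown. A further draw could be scheduled there.

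These points stand as limits on the claim. They do not overturn it: DXA and the inflammatory markers are named outcomes, so their repetition has support elsewhere, and CBC and CMP have none in the supplied text.

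It is also fair to say that the aims concern efficacy and mechanism, so no planned laboratory safety claim is left unsupported. The point is a cheap improvement, not a contradiction in the plan.

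A reader might infer more than the documents support:

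- **At least half of the exposure is unchecked.** The draw is only approximately at week 8, so the supportable wording is about half.
- **A late problem could neither be seen nor followed up.** Weekly contact, blood pressure, adverse-event evaluation and review of laboratory data continue. Hepatic triglyceride and fibrosis imaging is repeated, and blood and urine from before and after treatment are stored. None of this replaces the panel, but the absolute statement fails.
- **A week-8 result waits about two months for review.** If the interval in Section H is two months (about 8.7 weeks), a result could wait until week 8 + 8.7 = 16.7. The term could equally mean twice a month, the review is presented as an added layer, and nothing says that results are held for it.

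**Conclusion.** The point holds in limited form. In the supplied text, the last named CBC/CMP precedes about half of the dosing: 50% to 56% for a draw at week 8, or 44% to 61% under the assumed window of one week either side. The literal reading of C.3.2, C.3.7 and Section H gives no end-of-treatment panel. Section D specifies no safety comparison at any time point, which covers adverse events as well as bloods.

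This rests on two conditions: that the missing Sections F and G schedule no further draw, and that the repeat clause is read as written. If the sponsor confirms that the clause already includes the safety bloods, only the missing safety analysis remains. The primary analysis and sample size are not affected.

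**What to change.** 1. In C.3.7, state that the repeat clause covers CBC and CMP. If it does not, add both to a blood draw already taken at the post-treatment inpatient visits, while participants are still on study pills.
2. In Section D, add a summary by arm of laboratory change from screening to week 8 and from screening to end of treatment, with the number of participants contributing at each time, and a by-arm summary of adverse events.
3. In Section H, reconcile the description of safety monitoring as continuous with its stated bi-monthly interval, and define that interval. No review rule is proposed here.

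Cost: no extra visit is needed. The panels number at most 2 x 28 = 56, or about 2 x 22 = 44 if the planned 22 per group complete (28 less the 6 drop-outs allowed for). There are laboratory fees, some incidental abnormal values to follow up, and a short set of safety tables.

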a. Hyperinsulinemic-euglycemic clamp procedure. At ~0700h in the morning after admission, after subjects have fasted for ~11 hours overnight, an intravenous catheter will be inserted into an antecubital vein to infuse stable isotope tracers, insulin and dextrose. A second catheter will be inserted into a radial artery to obtain arterial blood samples. A primed-constant infusion of [6,6-²H₂]glucose and a constant infusion of [U-¹³C]palmitate will be started and maintained for 3.5 h to obtain basal glucose and fatty acid kinetics. At ~1030h, insulin will be infused for ~3.5 h at 50 mU/m² BSA/min (initiated with a two-step priming dose of 200 mU/m² BSA/min for 5 min followed by 100 mU/m² BSA/min for 5 minutes). Euglycemia (~100 mg/dL) will be maintained by variable rate infusion of 20% dextrose enriched to 2.5% with [6,6-²H₂]glucose. Adding glucose tracer to the dextrose infusion provides a more accurate measure of glucose kinetics by minimizing changes in plasma glucose enrichment [35]. The infusion rates of [6,6-²H₂]glucose and [U-¹³C]palmitate will be decreased by 75% during insulin infusion, because of the expected decreases in endogenous glucose production and palmitate release into the circulation. Blood samples will be obtained immediately before starting the tracer infusion and every 10 min during the final 30 min (4 samples) of the basal period and clamp procedure, to determine glucose and insulin concentrations and substrate kinetics. We have found this infusion protocol is well-tolerated by study subjects and is needed to achieve steady-state conditions in plasma glucose tracer enrichment during each stage.

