a. Substrate kinetics and insulin sensitivity. Glucose and palmitate kinetics during the clamp procedure will be used to provide an index of hepatic, skeletal muscle and adipose tissue insulin sensitivity, as we previously described [31, 38, 39]. Glucose Ra in plasma during basal conditions and the clamp procedure will be calculated by dividing the glucose tracer infusion rate by the average plasma glucose TTR during the last 30 min of the basal and clamp periods, respectively. Glucose Ra during basal conditions represents endogenous glucose Ra, an index of hepatic glucose production rate, which equals basal glucose rate of disappearance (Rd). During the clamp procedure, hepatic glucose production rate will be calculated by subtracting the glucose infusion rate (i.e., dextrose solution plus tracer added to it) from total glucose Ra (endogenous plus exogenous); glucose Rd is equal to total glucose Ra (i.e., the sum of endogenous glucose Ra and the rate of infused glucose). Palmitate Ra, an index of adipose tissue lipolysis will be calculated by dividing the palmitate tracer infusion rate by the average plasma palmitate TTR obtained during the final 30 min of the basal period and insulin infusion.

b. β -cell function. Insulin secretion rate (ISR) during the modified 3-h oral glucose tolerance test (MOGTT) will be calculated by stochastic deconvolution analysis of the plasma C-peptide concentration time-course [40]. β -cell response sensitivity to glucose will be assessed as the ratio of the area under the curve (AUC) of ISR (pmol/L) to the AUC of glucose [41-43]. β -cell function in relation to insulin sensitivity will be assessed based on the principle of the disposition index, calculated as the product of the area under the curve (AUC) of ISR (pmol/L) assessed during the MOGTT and the rate of insulin-stimulated glucose disposal normalized for plasma insulin concentration ($\mu\text{mol/kg FFM/min per } \mu\text{IU/mL}$) assessed during the hyperinsulinemic euglycemic clamp procedure, as we have previously reported [20]. Insulin secretory reserve will be assessed by measuring the AUC of insulin and ISR over 10 min after the intravenous administration of 5 g of arginine [44, 45].

C.3.9. Sample analyses.

All sample analyses are routinely performed by our research group or in our Core laboratories at Washington University School of Medicine.

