a. Plasma concentrations of substrates and hormones and markers of inflammation will be measured by our Core Laboratory for Clinical Sciences, as we have previously described [30, 32].

b. Plasma glucose and palmitate tracer-to-tracee ratios will be determined by using gas chromatography-mass spectroscopy, as we have previously described [46].

c. Plasma NMN and nicotinamide, PBMC NAD^+ and tissue NAD^+ , nicotinamide and ATP. Plasma NMN and nicotinamide and tissue NAD^+ , nicotinamide, and ATP concentrations will be determined by using an HPLC system (Prominence; Shimadzu) with a Supelco LC-18-T column (Sigma) and a Hypercarb column (Thermo Scientific), as we have previously described [2, 5, 7, 14, 47-51].

d. Adipose tissue gene expression of inflammatory markers (*IL6*, *TNF*, *MCP-1*, *IL1 β* , *EMR1*, *CD68*) and adiponectin (a key downstream target of adipose tissue NAD^+ [7]) will be determined by using Real time-PCR. Total RNA will be isolated from frozen adipose tissue biopsy samples in RNeasy kit (Qiagen, Valencia, CA) and reverse transcribed (High-Capacity cDNA Reverse Transcription Kit; Invitrogen, Carlsbad, CA) [30, 32,

52-56]. Tissue gene expression was determined using an ABI 7500 real-time PCR system (Invitrogen) and SYBR Green Master Mix (Invitrogen), as we have previously described [30, 32, 53]. The expression of each gene will be normalized to the housekeeping control gene, ribosomal protein (*RPLP0*).

e. Skeletal muscle transcriptome analysis by using RNA-seq. Total RNA will be isolated from frozen skeletal muscle biopsy samples in Trizol reagent (Invitrogen), as we have previously described [53-55, 57]. We will first evaluate the effects of NMN supplementation on muscle gene expression of specific NAD⁺ downstream targets (mitochondrially encoded genes, *ND1-ND6*, *Cytb*, *COX1*, *COX2*, *COX3*, *ATP6*, *ATP8*) [16] and inflammatory markers (*IL6*, *TNF*, *MCP-1*, *IL1 β* , *EMR1*, *CD68*) by using Real time-PCR as described above.

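### Taken literally, the clamp formula in C.3.8.a subtracts the tracer in the dextrose from an Ra that never counted it, so hepatic glucose production is understated by about 2.5% of the glucose infusion rate

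*Combined protocol and SAP*

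**What the plan says.** Section C.3.8.a gives one rule for glucose Ra, covering the basal and clamp periods alike: "dividing the glucose tracer infusion rate by the average plasma glucose TTR during the last 30 min of the basal and clamp periods". Section C.3.9.b confirms what the ratio is: "Plasma glucose and palmitate tracer-to-tracee ratios will be determined by using gas chromatography-mass spectroscopy". It is labelled over unlabelled glucose, not labelled over total.

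In the clamp (C.3.2.1.a), euglycaemia is held by "variable rate infusion of 20% dextrose enriched to 2.5% with [6,6-²H₂]glucose", the same tracer as in the constant infusion. The constant infusion continues at a rate reduced by 75%.

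For the clamp, C.3.8.a then states that "hepatic glucose production rate will be calculated by subtracting the glucose infusion rate (i.e., dextrose solution plus tracer added to it) from total glucose Ra", and it describes that total as covering both endogenous and exogenous glucose. For the quantity behind the primary outcome it states that "glucose Rd is equal to total glucose Ra (i.e., the sum of endogenous glucose Ra and the rate of infused glucose").

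C.3.8.a uses clamp hepatic production as its index of liver insulin sensitivity. Section B names the liver among the organs whose insulin sensitivity is to be assessed.

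**The concern.** A tracer rate divided by a tracer-to-tracee ratio returns the appearance rate of tracee, which is unlabelled glucose. With labelled dextrose, the infused label is not part of that result. Subtracting an infusion rate that includes the label therefore removes something that was never added.

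Hepatic production during a clamp is a small remainder between two large numbers, so a slip of 2.5% in the larger term matters in relative terms. The slip is also proportional to the glucose infusion rate, which rises with muscle glucose disposal. Participants with higher Rd would therefore show somewhat lower hepatic production for arithmetic reasons alone. At stake are the reported level of clamp hepatic production, its percent suppression from basal, and any correlation of either with Rd.

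The plan's internal balance would not expose the slip. The understated production plus the infused glucose (dextrose and its tracer) adds back exactly to tracer rate over TTR, so the books appear to close.

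**Working it through.** **The plan's own figure first.** Section D gives SD 6.1, detectable difference about 6.2, two-sided alpha 0.05 and 90% power. The normal approximation gives 21 per group and the noncentral t gives 22 (power 0.909), as planned. Adding 6 drop-outs gives 28, and 6.2/44.5 = 13.9%, matching the stated 14%. The documents give no figure for clamp hepatic production.

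**Inputs from the documents.** Expected baseline Rd 44.5 and design difference 6.2 µmol/kg FFM/min (section D); dextrose enrichment 2.5% (C.3.2.1.a).

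**Assumptions.** True clamp hepatic production E is not given; values from 0 to 10 are used. The constant tracer rate F0 during the clamp is not given; 0 to 0.1 is used. Whether 2.5% is a fraction of total glucose or a ratio to unlabelled glucose is not stated; both were run.

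**Algebra.** Let G be the dextrose infusion including its tracer, f the tracer fraction, and F = fG + F0 all infused tracer. At steady state:

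- TTR = F / (E + (1 − f)G), so F/TTR = E + (1 − f)G.
- Literal rule: F/TTR − G = E − fG.
- The error is −fG, the tracer carried in the dextrose. F0 affects it only slightly, through G.

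**Worked case** (Rd 44.5, E = 2, F0 = 0, f = 0.025):

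- G = 44.5 − 2 = 42.5, and F = 0.025 × 42.5 = 1.0625.
- TTR = 1.0625/43.4375 = 0.02446, and F/TTR = 43.4375.
- Literal rule: 43.4375 − 42.5 = 0.94, against a true value of 2.00.
- Subtracting unlabelled dextrose only: 43.4375 − 41.4375 = 2.00.
- A numerical integration of a one-pool model to steady state gave the same TTR and the same 0.94.

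**Size at Rd 44.5** (f = 0.025, F0 = 0):

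| Assumed true production | G | Understatement | Literal result |
|---|---|---|---|
| 0 | 44.5 | 1.11 | −1.11 |
| 2 | 42.5 | 1.06 | 0.94 |
| 3.0 | 41.5 | 1.04 (35%) | 1.96 |
| 4.5 | 40.0 | 1.00 (22%) | 3.50 |
| 5 | 39.5 | 0.99 | 4.01 |
| 10 | 34.5 | 0.86 | 9.14 |

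If 2.5% is a ratio to unlabelled glucose, f = 0.025/1.025 = 0.0244 and the understatement runs from 0.84 to 1.09.

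**Percent suppression.** The residuals of 3.0 and 4.5 correspond to an assumed basal production of 12 and 18 with 75% suppression. The literal rule would show 1 − 1.96/12 = 84% and 1 − 3.50/18 = 81%.

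**Between groups.** If Rd is 6.2 higher and true production is unchanged, the extra understatement is 0.025 × 6.2 = 0.155. With E = 2, the literal result moves from 0.94 at Rd 44.5 to 0.78 at Rd 50.7.

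**Primary Rd.** Taken as F/TTR, Rd is low by F. Across the scenarios at 44.5 this ranges from 0.84/44.5 = 1.9% to 1.21/44.5 = 2.7%. Because it is nearly a constant factor, it scales the difference and the SD alike. The standardised difference 6.2/6.1 = 1.02 is essentially unchanged, and so are the 22 and 28 per group.

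**The case against.** The strongest reply is that C.3.8.a describes total Ra as covering both endogenous and exogenous glucose, and Rd as including the rate of infused glucose, having just defined that rate as dextrose plus its tracer. If total Ra contains the label, subtracting dextrose plus label is a sound mass balance. The section also refers to earlier published methods, and the laboratory may add the tracer rate back in practice. This stands as far as it goes: the documents do not show that the laboratory will compute the wrong number. But no stated step adds the tracer, and the only Ra formula given is tracer rate over TTR. An analyst who follows the text gets the understated value.

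Two stronger readings are tempting, and the documents support neither.

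- A reader might infer that a purely muscular effect would pass for a liver effect and undo the multi-organ goal. Clamp hepatic production is not among the outcomes listed in C.3.1, Aim 1(ii) specifies adipose tissue and skeletal muscle, and most of the offset is common to both arms. The differential part, 0.155, is too small to carry that claim.
- A reader might infer that the tracer rate means only the constant infusion that is cut by 75%, which would badly understate primary Rd. Nothing states that definition, and C.3.2.1.a says tracer is added to the dextrose to measure kinetics more accurately. The term is undefined and should be defined, but this is not a separate error.

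It is also fair that the percentages depend on residual production values that the documents do not give.

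**Conclusion.** The point holds as a defect in the written calculation. As stated, the rule understates clamp hepatic glucose production by the tracer in the dextrose, about 2.5% of the glucose infusion rate, and it disagrees with the verbal definitions beside it. The absolute error at the expected Rd, about 0.9 to 1.1 µmol/kg FFM/min, depends little on the assumptions. The relative error of 22–35% rests on an assumed residual of 3.0–4.5, and all figures take the tracer rate to include the label in the dextrose.

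Materiality is modest. The level and percent suppression of hepatic production would be wrong if reported. The treatment comparison of that index would be biased only slightly, and the primary comparison and the sample size are not affected in substance.

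**What to change.** Rewrite the calculation in C.3.8.a so that formula and definitions agree:

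- F = all infused tracer, that is, the constant infusion plus the tracer in the dextrose.
- Hepatic glucose production = F/TTR minus the unlabelled dextrose infusion rate. Equivalently, F/TTR + F minus all infused glucose including all tracer.
- Total Rd = (F/TTR) × (1 + TTR).
- State whether the 2.5% enrichment is a fraction of total glucose or a ratio to unlabelled glucose.
- Apply the same code at the baseline and 16-week clamps.

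If the laboratory already works this way, only the text changes. Otherwise the code changes too. No new samples, measurements or visits are needed, and the sample size stays as it is.
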